At select institutions, patients will be required to undergo a repeat tumor biopsy at the time of disease progression following an initial response. Repeat biopsies will be obtained **only** from patients who have disease progression after one of the following treatment responses:

- Objective response (complete or partial response), or
- Stable disease \geq 6 months.

The biopsy site should be chosen based on safety and the presence of tumor growth at that site. Afatinib and cetuximab do not need to be held around the time of the biopsy. See [Section 15.5](#) and [15.6](#) for more details.

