15.4 Prestudy tissue

The submission of tissue is required for all patients. Submit within 28 days after registration. Kits are not provided for these specimens.

Submit one or two paraffin-embedded tissue blocks containing formalin fixed tumor and corresponding hematoxylin and eosin (H&E) slide. Submission of blocks is strongly encouraged. However, if blocks are unavailable, 15-20 unstained slides are acceptable alternatives (12 absolute minimum, 20 strongly encouraged). Cytology (e.g. fine-needle aspirations, pleural effusion specimens) can be accepted only if they are paraffin embedded as cell blocks, positive for malignant cells, and provide sufficient number of required blocks or slides.

Tumor material must be reviewed by a local pathologist to ensure at least 100 viable tumor cells are present in the sample (the estimate must be noted in the **S1403** Local Pathology Review Form [[Section 18.3](#)]). The local pathologist must review and sign the **S1403** Local Pathology Review Form. The **S1403** Local Pathology Review Form and pathology report must be submitted with the specimen to the SWOG Solid Tumor Repository and must be uploaded via the Source Documentation: Baseline in Rave®.

If a new biopsy is necessary at baseline due to insufficient tissue, in addition to the requisite formalin-fixed paraffin embedded tissue, a portion of the biopsy should be retained as fresh-frozen tissue, if feasible. Tissue (e.g. 1-2 cores, pleural effusion cell pellets, bronchoscopy forceps biopsies, etc.) should be immediately flash frozen in liquid nitrogen and stored at -80°C until shipped on dry ice.

Refer to the general labeling, packaging, and shipping instructions at <http://swog.org/Members/ClinicalTrials/Specimens/STSpecimens.asp> and **ship to Lab #201** (SWOG Specimen Repository - Solid Tissue, Myeloma and Lymphoma Division - see the Specimen Tracking System).

15.5 Additional requirements for sites participating in the repeat biopsy study, *but not* in the patient-derived xenograft (PDX) study

This section only applies to those sites participating in the repeat biopsy study, but not in the patient-derived xenograft (PDX) study. For a list of these sites, please refer to the Activation notice distributed April 1, 2015 and any subsequent memoranda.

Kits are not provided for these specimens.

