18.1 Translational Medicine

The primary translational objectives of this study are to understand mechanisms of sensitivity and resistance to afatinib plus cetuximab and afatinib alone in the front-line treatment setting in patients with *EGFR* mutation positive lung cancer. The goals are to study pre-treatment tumor samples (required from all patients on the trial) to understand mechanisms of sensitivity to these agents and to compare pre-treatment and repeat biopsy specimens at progression (obtained from a subset of patients on the trial at specific designated institutions as discussed below) to investigate the molecular mechanisms of resistance to these drugs and to devise strategies to overcome them. See [Section 15.0](#) for details regarding tissue collection.

All patients enrolled in the therapeutic trial will be eligible for these studies. *Pre-treatment* specimens will have been processed as per standard of care for formalin fixation and paraffin-embedding at individual institutions and are required for enrollment on the trial. Submission of a *repeat biopsy* specimen at progression on afatinib plus cetuximab or afatinib alone will be required at only a subset of institutions participating in the Repeat Biopsy Sub-Study. Our goal is to collect repeat biopsies from 100 patients (approximately 50 patients on each arm of the study). In cases with limited tissue, priority will be given to studies as listed in order below (i.e. *EGFR* T790M testing will have highest priority, then copy number alterations, etc.).

The translational medicine studies proposed are described below *in order of priority*.

a. EGFR T790M mutation analysis (INTEGRATED)

Background, hypotheses and objectives: In *EGFR* mutant lung adenocarcinomas, resistance to *EGFR* TKIs is most frequently associated (50-60% of cases) with the emergence of a secondary mutation in *EGFR*: the *EGFR* T790M mutation. Using tetracycline inducible transgenic mouse models of *EGFR* mutant lung cancer harboring the erlotinib-resistant T790M mutation, it has been shown that that combined treatment with the irreversible TKI, afatinib, and the antibody to *EGFR*, cetuximab, caused these tumors to

regress dramatically whilst neither drug alone was effective ([Figure 1](#)). (1)

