To evaluate if the ratio of EGFR sensitizing mutation to EGFR T790M mutation (EGFRs/EGFR T790M) among patients with T790M is predictive for afatinib monotherapy, analyses will be performed in a similar fashion to the evaluation of T790M among patients with measurable T790M (which defines T790M). Cox regression will be used to assess the predictive association of the ratio in the afatinib monotherapy arm with both OS and PFS. Further analyses will evaluate a differential effect by including an interaction term for treatment x EGFRs/EGFR T790M ratio among all patients randomized to either afatinib plus cetuximab or afatinib alone with EGFR T790M.

3. Compare the ratio of sensitizing EGFR mutation to EGFR T790 mutation between tissue collected at re-biopsy after progression to baseline.

To evaluate if EGFRs/EGFR T790M is lower at progression than in pre-treatment specimens among patients with results available for pre-treatment and progression, a one-sample t-test (or Wilcoxon signed-rank test) will be used to test the null hypothesis that the difference between the progression ratio and the pre-treatment ratio (or an appropriate transformation of the difference, determined after exploratory data analysis) is greater than zero in favor of the alternative that the difference is less than zero.

We will evaluate the emergence of EGFR T790M mutations in patients who progress after an initial response to treatment (defined as complete or partial response or stable disease for ≥ 6 months). Post-treatment tissue specimens will be collected on 100 patients, approximately 50 on each treatment arm, and it is assumed that at most 35% of these patients will have a T790M mutation at baseline. It is further assumed that approximately 50% of patients on the single agent afatinib arm will have developed T790M mutations at the time of resistance. Thus, if we assume approximately 33 patients per arm, using a binomial test of proportions with a one-sided alpha of 0.10, there will be at least 80% power (depending on the de novo prevalence) to detect a difference of 30% between treatment arms.

b. Copy number alterations in *MET*, *EGFR* and *HER2* (INTEGRATED)

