Background, hypotheses and objectives: Resistance to EGFR TKIs is most frequently associated (50-60% of cases) with the emergence of the *EGFR* T790M mutation. (9) In addition, bypass mechanisms that activate parallel or downstream signaling pathways such as ***amplification of the receptor tyrosine kinase (RTK) genes MET and HER2***, activation of AXL or mutations in *PIK3CA* and *BRAF* have also been observed in the setting of TKI resistance. (10, 11, 12, 13, 14, 15, 16) Moreover, amplification of the *EGFR* allele harboring the T790M mutation was observed in a subset of TKI-resistant *EGFR* mutant lung

adenocarcinomas. (17) In view of the evidence implicating *MET*, *HER2* and *EGFR* in resistance to first generation TKIs, ***we hypothesize that amplification of the receptor tyrosine kinases, EGFR, HER2 and MET may contribute to both decreased sensitivity and acquired resistance to afatinib plus cetuximab and afatinib alone.*** Moreover, since these drugs target *EGFR* (afatinib and cetuximab) and *HER2* (afatinib), it is likely that tumor escape mechanisms will involve these receptors in at least a fraction of cases.

Our **objective** is to determine if amplification of the receptor tyrosine kinases, *EGFR*, *HER2* and *MET* contributes to both decreased sensitivity and acquired resistance to afatinib plus cetuximab and afatinib alone.

Preliminary Data: Data in the literature support the role of amplification of these receptor tyrosine kinases as indicated above. Moreover, unpublished data from our analyses of repeat biopsies with resistance to EGFR-directed therapies (including afatinib plus cetuximab) at Yale, has uncovered amplification of these RTKs.

Research Design and Methods: Pre- and post-treatment tissue will be analyzed for alterations in *MET*, *EGFR* and *HER2* using Fluorescence In Situ Hybridization (FISH) performed by the CLIA-certified Yale Cancer Center Molecular Diagnostics Laboratory by [name] in formalin-fixed paraffin embedded (FFPE) tissues at baseline and at the time of acquired resistance to afatinib plus cetuximab or afatinib alone (the former only for the 100 patients on the repeat biopsy portion of the study). The following probe sets will be used for these studies:

- a. *MET* gene (FISH analysis): C-MET (7q31)/SE7 probe (Cat# KI-10719, Kreatech, Durham, NC).
- b. *HER2* gene (FISH analysis): Vysis_PathVysion™ HER-2 DNA Kit (Cat# 02J01-036, Abbott Laboratories, Abbott Park, Illinois).

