- c. *EGFR* gene (FISH analysis): EGFR, HER-1 (7p11)/SE7 probe (Cat# KI-10702, Kreatech, Durham, NC).

For copy number analysis of *EGFR*, *MET* and *HER2*, two 5um sections mounted on charged slides will be used for each FISH assay (a total of 6 slides pre-treatment and 6 slides from the re-biopsy at progression). The ratio of specific gene signals to centromeric probe signals will be used to calculate copy number. For all three genes, a ratio >2.0 is interpreted as amplification of the gene if at least 50 nuclei are counted based on current literature. (18, 19, 20, 21)

[name] is the key contact for questions regarding this translational medicine study:

[name]
Department of Pathology
Yale University School of Medicine
[name]
[name]
Email: [contact]

Statistical Design:

1. To evaluate the prognostic role of these molecular alterations (e.g. *MET*, *EGFR* or *HER2* amplification) for *resistance* to afatinib plus cetuximab or afatinib alone.

For each potential marker, a logrank test at the 5% level will be used to compare OS and PFS between patients with amplification versus patients without amplification. The following table details the power to detect a two-fold difference in median PFS using a 2-sided 0.10 level logrank test across a range of possible marker prevalence.

Marker prevalence	Power
5%	73%
10%	93%
15%	98%
20%	99%

HER2 amplification is expected to be seen in approximately 1% and *MET* amplification in 3% of patient specimens at baseline. The relationship between OS, PFS and these abnormalities will be evaluated as above, although the power to detect differences is expected to be low.

Further comparisons will be performed within treatment arms. To assess a differential effect by treatment arm, Cox regression will be used to test treatment interaction, again using OS and PFS as the outcome.

To evaluate the prognostic role of other molecular alterations (e.g. *MET*, *EGFR* or *HER2* amplification) for *sensitivity* to afatinib plus cetuximab or afatinib alone, for each potential marker, a chi-squared or Fisher's exact test at the 5% level will be used to compare response rates between patients with amplification versus patients without amplification.. The following table details the power to detect a 30% difference in response rates using a 1-sided 0.05 level test across a range of possible marker prevalence.

Marker prevalence	Power
5%	46%
10%	76%
15%	90%
20%	95%

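### The Section 18.1b methods confine baseline FISH to the 100 repeat-biopsy patients, contradicting the tissue rules and the item 1 marker analyses; probably a former/latter slip

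*Combined protocol and SAP*

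**What the plan says.** The Research Design and Methods paragraph of Section 18.1b plans FISH at two times, baseline and acquired resistance, and then qualifies it: "the former only for the 100 patients on the repeat biopsy portion of the study". Of the two times listed, the former is baseline.

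Other parts of the protocol describe the specimens differently:

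- **Section 18.1, opening:** "The goals are to study pre-treatment tumor samples (required from all patients on the trial"), to understand sensitivity. The repeat biopsy comes from designated institutions only: "Our goal is to collect repeat biopsies from 100 patients (approximately 50 patients on each arm of the study").
- **Section 15.4:** "The submission of tissue is required for all patients".
- **Section 7.4d:** repeat biopsies are taken only "from patients who have disease progression after one of the following treatment responses", namely an objective response or stable disease of at least 6 months. The statistical design of Section 18.1a uses the same group: "patients who progress after an initial response to treatment (defined as complete or partial response or stable disease for ≥ 6 months").
- **Section 18.1b, statistical design, item 1:** a logrank test "will be used to compare OS and PFS between patients with amplification versus patients without amplification", and a chi-squared or Fisher's exact test does the same for response. No repeat-biopsy restriction appears. The expected frequencies are baseline ones: HER2 about 1%, and MET "amplification in 3% of patient specimens at baseline".
- **Section 18.1b, statistical design, item 2:** the paired comparison before and after treatment is limited to patients who progress after an initial response.

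**The concern.** The parenthesis is the only explicit statement in Section 18.1b of who receives baseline FISH. The stated objective covers decreased sensitivity as well as acquired resistance. A patient with primary resistance, meaning no response and progression before 6 months, never qualifies for repeat biopsy. Under the literal rule that patient would have no baseline FISH result.

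The item 1 tests of PFS and response would then run in patients chosen partly for their PFS and response. Non-responders would enter only after at least 6 months of stable disease, and everyone in the set would have progressed. The number tested would also be smaller than the printed power assumes. Item 2 mentions both specimens only for patients who progress after an initial response. That is correct for a paired analysis, but it could reinforce the restrictive reading for a laboratory working from this section alone.

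**Working it through.** **1. Which reading fits the other sections?**

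| Specimen | Literal Section 18.1b | Sections 15.4, 18.1 (opening) and 7.4d |
|---|---|---|
| Baseline | only the 100 repeat-biopsy patients | required from all patients |
| Progression | no limit stated | only the repeat-biopsy subset, goal 100 |

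The two columns are reversed. The parenthesis also stands next to another pair, the two treatment arms. It cannot refer to that pair, because the 100 are split about 50 per arm.

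**2. Reproducing the PFS power table in item 1.** The inputs given there are a two-fold difference in median PFS (hazard ratio 0.5 under exponential survival), a two-sided 0.10 logrank test, and marker prevalence p. No event count D is stated. By Schoenfeld's approximation:

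power = Φ( √(D·p·(1−p)) × ln 2 − 1.645 )

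Solving for D from the printed powers of 73%, 93% and 98% gives 223, 225 and 223. The 99% row gives 205, but that entry is sensitive to rounding. At p = 5% and D = 225: √(225 × 0.0475) = 3.269; × 0.693 = 2.266; − 1.645 = 0.621; power 73%.

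| D | p = 5% | 10% | 15% | 20% |
|---|---|---|---|---|
| Printed in the plan | 73% | 93% | 98% | 99% |
| 225 | 73% | 93% | 98% | 99% |
| 100 (literal rule, every patient with an event) | 45% | 67% | 80% | 87% |
| 170 (80% of 212, every patient with an event) | 63% | 86% | 94% | 98% |

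All four printed entries are matched within 2 points for D from 215 to 230, so the table was not built on 100 patients. It equals the PFS column of the Section 18.1a table for the afatinib arm, where about 230 patients per arm were expected to have baseline results.

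The last row is there for fairness. Section 18.1a's 460 baseline results predate the reduction to 212 eligible patients. Applying the plan's own 20% assay loss gives 0.8 × 212 = 170. Part of the fall from 73% to 45% therefore comes from the smaller trial. At 5% prevalence the literal wording accounts for the step from at most 63% to at most 45%.

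**3. The response power table.** The plan prints 46/76/90/95% for a 30-point difference at one-sided 0.05, with no base rate. Assuming 70% against 40%, one-sided Fisher's exact test with 195 patients (85% measurable of 230) gives 46/77/89/95%. With 100 patients and the same rates it gives 20/45/60/73%. The base rate is my assumption. Over base rates from 20% to 56% and 85 to 100 patients, power runs from about 1% to 35% at 5% prevalence and from 64% to 82% at 20%.

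**4. Expected amplified cases at baseline.**

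| Patients with baseline FISH | HER2 (1%) | MET (3%) |
|---|---|---|
| 100 | 1.0 | 3.0 |
| 170 | 1.7 | 5.1 |

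The 100-patient row applies unselected prevalences to a selected group, so it is only indicative. No baseline prevalence is given for EGFR amplification.

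**5. How many could be lost through early progression?** Section 11.1 assumes afatinib PFS medians of 13.7 months (56% of patients, exon 19) and 10.8 months (44%, L858R). The share with progression or death by 6 months is 1 − (0.56 × 0.5^(6/13.7) + 0.44 × 0.5^(6/10.8)) = 1 − 0.713 = 29%. This is an upper bound for exclusion by this route in the afatinib arm, because a responder who progresses before 6 months still qualifies for repeat biopsy.

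**The case against.** The strongest reply is that the literal sentence defeats itself. If only the baseline assay is restricted, FISH at progression is unrestricted, yet progression tissue is collected only from the subset. The sentence would order assays on tissue that does not exist and withhold them from tissue every patient must submit. The intended design can be recovered from Section 18.1 and from the power tables, so a competent laboratory would probably ask. In addition, Section 18.1b already concedes low power for HER2 and MET, and no primary or secondary objective is touched.

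Most of this stands. It shows a wording slip, not a design decision, and it limits the severity. It does not make the text safe to leave. The sentence is an operative instruction, nothing else in Section 18.1b corrects it, and the intended population has to be inferred from other sections and from back-solved tables.

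A reader might go further and infer that baseline amplification cannot be tested against PFS or response at all, or that the tests are biased toward no association. The documents support neither inference. A test in 100 patients remains possible, though selected and weaker. The direction and size of any bias depend on how amplification relates to early progression, which the plan does not give and which has not been computed.

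**Conclusion.** The contradiction is real and is best read as *former* written for *latter*. Taken literally, the rule would replace the item 1 population with an outcome-selected set of about 100, with PFS power of at most 45/67/80/87% against the printed 73/93/98/99%. Taken as evidently intended, the printed tables are reproducible on the basis of about 230 patients in one arm, although that basis itself predates the reduction to 212.

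Three assumptions carry the arithmetic. The event count is back-solved, and a D near 225 would mean an event in nearly every patient of one arm. The D = 100 row takes the best case, in which all 100 contribute an event. The response base rate is assumed. The contradiction itself rests only on the text. Severity is minor to moderate: it affects an integrated translational objective, and power for HER2 and MET is low under either reading.

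**What to change.** In the Section 18.1b methods, change *the former* to *the latter*. It is safer to name the specimen, because the words also sit beside the pair of treatment arms. For example: FISH will be performed on baseline tissue from all patients with adequate tissue, and on progression tissue from patients in the repeat biopsy portion only.

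In the statistical design, state that the item 1 analysis set is all patients with adequate baseline tissue, and that only the paired comparison in item 2 is limited to repeat-biopsy patients.

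The cost is a sentence or two. Baseline tissue is already required from everyone, six pre-treatment slides are already allotted to FISH, and the extra baseline assays are those item 1 already presupposes.

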1.3 Translational Objectives

- a. To investigate the molecular mechanisms that confer benefit from afatinib and afatinib plus cetuximab by evaluating whether the presence of *de novo EGFR T790M* mutation or other molecular alterations in the pre-treatment tumor influence the clinical outcomes
- b. To quantitatively assess whether the ratio of sensitizing *EGFR* (*EGFRs*) mutation to *EGFR T790M* influences outcome and is altered during treatment.
- c. To evaluate the frequency of known mechanisms of resistance to EGFR-directed therapies in the context of afatinib plus cetuximab and afatinib alone treatment.
- d. To identify potential novel predictors of benefit to afatinib plus cetuximab.
- e. To identify potential new mechanisms of resistance to EGFR-directed therapies.
- f. To establish patient-derived xenografts (PDXs) from a subset of patients by re-biopsy at the time of progressive disease for drug testing and genomic analysis.
- g. To assess whether circulating tumor markers can be used as indicators of sensitivity and resistance to afatinib plus cetuximab and afatinib alone.
- h. To determine whether the levels of EGFR protein by immunohistochemistry predict for benefit to afatinib plus cetuximab and afatinib alone.

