2. **Compare copy number alterations in MET, EGFR, and HER2 between tissue specimens collected after disease progression and pretreatment tissue specimens**

Pre- and post-treatment tissue will be analyzed for alterations in *MET*, *EGFR* and *HER2* using Fluorescence in situ Hybridization (FISH) among those patients who progress after an initial response. *EGFR*, *MET*, and *HER2* amplification in patients with acquired resistance are expected in approximately 5%, 5%, and 12% of cases, respectively. For each of these markers, a one-sample t-test (or Wilcoxon signed-rank test) will be used to test the null hypothesis that the absolute difference between the copy number after progression and the copy number in the pre-treatment specimen (or an appropriate transformation of the difference, determined after exploratory data analysis) is not equal to zero.

c. **Whole exome sequencing of pre- and post-treatment specimens (INTEGRATED).**

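### FISH at progression (18.1b item 2) is analysed only as average copy-number change with no arm term, so the amplification part of objective 1.3c has no planned frequency or by-arm estimate

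*Combined protocol and SAP*

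**What the plan says.** Objective 1.3c is "To evaluate the frequency of known mechanisms of resistance to EGFR-directed therapies in the context of afatinib plus cetuximab and afatinib alone treatment". Section 18.1 aims for repeat biopsies from 100 patients, about 50 per arm.

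Section 18.1b treats amplification as present or absent: "a ratio >2.0 is interpreted as amplification of the gene if at least 50 nuclei are counted". Item 2 of its Statistical Design covers paired FISH specimens "among those patients who progress after an initial response". For EGFR, MET and HER2, in that order, "amplification in patients with acquired resistance are expected in approximately 5%, 5%, and 12% of cases, respectively". The analysis is then: "For each of these markers, a one-sample t-test (or Wilcoxon signed-rank test) will be used", on progression minus pre-treatment copy number or a transformation of it. The item gives no arm term, no proportion amplified, no significance level and no power.

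Two other analyses of progression biopsies do use the arms. Section 18.1a item 3 plans a binomial test of T790M emergence at one-sided 0.10, with about 33 patients per arm and at least 80% power "to detect a difference of 30% between treatment arms". Section 18.1c gives mutations at progression an exact 95% confidence interval on each arm.

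**The concern.** The objective names a frequency under each regimen. The planned test addresses the average shift in copy number. A significant result would show that copy number changed somewhere among the patients tested. It would not show how many tumours crossed the 2.0 threshold, or under which treatment.

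Section 18.1b itself notes that both drugs target EGFR while HER2 is targeted by afatinib, so the route of escape under each regimen is of scientific interest. If the plan is followed as written, any split by arm becomes an unplanned choice made after the data are seen.

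**Working it through.** **1. Does another section fill the gap?**
- 18.1b item 1 promises comparisons within arms and a Cox treatment interaction, but both relate amplification status to OS and PFS.
- 18.1c says the incidence of the major resistance mechanisms will be established as already described. For amplification, nothing before it estimates incidence.
- 18.1e models circulating marker levels over time and names no arm term.
- The landmark Cox model in 18.1f relates post-randomisation biomarkers to PFS and OS.

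None gives the frequency of acquired amplification by arm.

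**2. The plan's own figures for progression biopsies.** Item 2 has no figure to reproduce, so I checked its neighbours.
- 18.1c precision with 50 per arm: 1.96 × √(0.25/50) = 13.9%, matching the stated 14%.
- 18.1a T790M power with 33 per arm, one-sided 0.10: 50% v 20% gives 91.0% (Fisher 85.9%); 65% v 35% gives 88.7%. Both are consistent with at least 80%.

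**3. What the paired test responds to.** Assumptions, not in the documents: 100 pairs (50 per arm), noise SD 0.3 per ratio, a jump of 2.0 in a tumour that acquires amplification, two-sided 0.05. The overall rate is the plan's 12% for HER2. The expected mean change is 2.0 × (rate in arm 1 + rate in arm 2)/2, which is 2.0 × 0.12 = 0.24 in every row.

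| Acquired rate by arm | Paired t-test rejects | Between-arm z test, one-sided 0.10, rejects |
|---|---|---|
| 12% v 12% | 90% | 10% |
| 20% v 4% | 91% | 91% |
| 24% v 0% | 91% | nearly 100% |

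The signed-rank version rejects in 48% to 52% in all three rows. The absolute rates depend on the assumed SD and jump. The insensitivity to arm does not, because the test has no arm term. The last column uses the T790M level only to show that the specimens carry the information.

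**4. What by-arm reporting would give, at 50 per arm.**
- Expected amplified cases per arm: 0.05 × 50 = 2.5 (EGFR, MET) and 0.12 × 50 = 6 (HER2).
- Exact (Clopper-Pearson) 95% intervals: 2/50 gives 0.5% to 13.7%; 6/50 gives 4.5% to 24.3%.
- Approximate 95% half-width for a difference, 1.96 × √(2p(1−p)/50): 8.5 points at p = 5%, 12.7 points at p = 12%.

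**5. How large a difference a test could detect.** Rate needed in the other arm for 80% power:

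| Per arm | Test level | Against 5% | Against 12% |
|---|---|---|---|
| 50 | two-sided 0.05 | 24.7% | 35.6% |
| 50 | one-sided 0.10 | 18.6% | 29.0% |
| 33 | two-sided 0.05 | 31.1% | 42.1% |
| 33 | one-sided 0.10 | 22.9% | 33.7% |

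For smaller contrasts at 50 per arm, even one-sided 0.10 gives 49% for 16% v 8% (Fisher 38%), 59% for 8% v 2% (Fisher 31%) and 39% for 7% v 3% (Fisher 17%).

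**The case against.** A reader might infer that objective 1.3c cannot be answered at all. The documents do not support that. The objective asks for frequency, states no between-arm test and is not limited to FISH. T790M, which the plan calls the most frequent mechanism (50-60% of cases with EGFR TKIs), has a powered comparison between arms, and exome mutations have per-arm intervals.

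A reader might also infer that the plan chose to pool the arms. Item 2 never says so; it is silent on arm.

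The different handling of FISH also has a rationale. The plan expects an arm difference for T790M emergence and for certain mutations. For amplification it hypothesises only a contribution to resistance under both regimens, and a before-and-after test suits that. It follows that no direction is given for amplification, so the one-sided 0.10 level cannot simply be borrowed from T790M. Applied to three genes it would carry up to 1 − 0.9³ = 27% familywise error if the tests were independent.

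Finally, the simulation largely restates that a test without an arm term ignores arm, its contrasts are extreme, and power for modest differences is low.

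All of this stands, and it limits the point to amplification and the remedy to estimation. It does not supply the missing frequency: a test of average change produces no proportion amplified, overall or by arm.

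**Conclusion.** The point holds for the amplification component of objective 1.3c. The one analysis written for FISH at progression does not produce the quantity that the objective names, and no other section does. It is a mismatch of estimand within a translational substudy. The primary and secondary endpoints, patient safety and specimen collection are unaffected, and the proportions could be computed from the planned data.

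The sizes rest on 50 evaluable pairs per arm; the target of 100 biopsies is not re-justified after section 11.2c reduced the trial to 212 patients. They also treat 5%, 5% and 12% as rates of newly acquired amplification. Section 18.1b item 1 expects about 1% (HER2) and 3% (MET) amplified at baseline, so the newly acquired rates may be somewhat lower.

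**What to change.** In 18.1b item 2:
- For each gene, define acquired amplification as a FISH ratio of 2.0 or below at baseline and above 2.0 at progression, among patients with both results.
- Report the proportion in each arm with an exact 95% CI, and the between-arm difference with its CI. Label this exploratory and led by estimation. Make any test two-sided.
- Keep the paired change test as a supporting analysis, reported by arm. Correct its null hypothesis, which is currently worded as a difference not equal to zero.

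The cost is wording only, with no new specimens or assays. The drawback is imprecision: the intervals will be wide, and the text should say that only large differences could be detected, particularly for EGFR and MET.
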